3.0 ELIGIBILITY

3.1 Inclusion Criteria

- 3.1.1 ≥ 18 years old at diagnosis.
- 3.1.2 ECOG Performance Status 0, 1, or 2.
- 3.1.3 Biopsy-proven diagnosis of rectal adenocarcinoma.
- 3.1.4 Clinical AJCC 7th edition stage T2N1M0, T3N0M0 or T3N1M0 based on physical examination, CT scan chest [or chest x-ray AND CT abdomen or MRI abdomen AND pelvic MRI or endorectal ultrasound \(ERUS\)](#).
- 3.1.5 Preoperative lower gastrointestinal endoscopy (proctoscopy, sigmoidoscopy, colonoscopy) confirming tumor extent as no less than 5 cm and no greater than 12 cm from the anal [canal](#). If endoscopy is not rigid, CT or MRI can be used to indicate location from anal [canal](#).
- 3.1.6 Evaluation by a surgical oncologist, radiation oncologist, and medical oncologist ≤ 28 days prior to registration.
- 3.1.7 Confirmation that the patient is able to undergo a low anterior, sphincter-sparing resection with total mesorectal excision ≤ 28 days prior to registration.
- 3.1.8 In the absence of treatment on a clinical trial, the patient would be recommended to receive neoadjuvant chemoradiation followed by curative intent surgery.
- 3.1.9 The following laboratory values obtained ≤ 14 days prior to registration:
 - Absolute neutrophil count (ANC) $\geq 1500/\text{mm}^3$.
 - Platelet count $\geq 100,000/\text{mm}^3$.
 - Hemoglobin > 8.0 g/dL. May transfuse to meet eligibility.
 - Total bilirubin ≤ 1.5 x upper limit of normal (ULN).
 - SGOT (AST) ≤ 3 x ULN.
 - SGPT (ALT) ≤ 3 x ULN.

- Creatinine $\leq 1.5 \times$ ULN.

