5.1 Chemotherapy

Neoadjuvant FOLFOX (5-FU + leucovorin + oxaliplatin)

This regimen will be repeated every 2 weeks for 6 cycles; (1 cycle = 14 days).

Given first: Oxaliplatin 85 mg/m^2 IV in D5W 500 mL over 2 hours, Day 1

Given second: Leucovorin 200 mg/m^2 IV bolus in D5W 250 mL over 2 hours, Day 1

Given third: 5-FU 400 mg/m^2 IV bolus in a syringe given over 5–15 minutes, Day 1, then $2,400 \text{ mg/m}^2$ in 240 mL of 0.9% Sodium Chloride via continuous IV infusion over 48 hours, Days 1–2

Note: Oxaliplatin is administered first, prior to leucovorin; alternatively leucovorin may be administered (via separate infusion containers) concurrently with oxaliplatin.

5.1.1 If necessary to accommodate holidays, patient schedule or other justified circumstance approved by the PI, the schedule may be modified by \pm 3 days.

5.1.2 Chemotherapy dose modification is at the discretion of the treating medical oncologist, although any patient who requires dose modification below dose level -2 will be removed from study participation. There are no restrictions on dose modifications for the sixth cycle of FOLFOX.

5.1.3 Patients who cannot tolerate 6 cycles of FOLFOX or those who require dose modification below dose level -2 or those who are found to be ineligible for the study based on central review of either the baseline or the follow up MRI or those that withdraw consent will receive preoperative combined modality chemoradiation with infusional 5-FU. There are no restrictions on dose modifications for the 6th cycle of neoadjuvant FOLFOX.

5.1.4 Patients receiving oxaliplatin on this study should be counseled to avoid cold drinks, chewing ice chips, and exposure to cold water or air because the sensory neurotoxicity often seen with oxaliplatin appears to be exacerbated by exposure to cold. The period of time during which the patient appears to be at risk for these cold-induced sensory neuropathies is not well documented. Patients should exercise caution regarding cold exposure during the treatment period. Peripheral sensory neuropathies can occur at any time after receiving oxaliplatin therapy.

5.1.5 Concurrent medications are at the discretion of the treating physician.
Current Greenebaum [Comprehensive](#) Cancer Center recommended:
Ondansetron 16 mg PO daily, if patient unable to take orally give 8 mg IV.
Dexamethasone 12 mg PO daily, if; unable to take orally give IV.

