11.0 DOSE MODIFICATION BASED ON ADVERSE EVENTS

11.1 Radiation therapy

Treatment interruptions are discouraged although may be necessary due to acute severe complications. Documentation must be made for any such complications including the reason and length of the treatment interruption.

If chemotherapy is held, then radiation therapy will be held. If radiation is held, then chemotherapy would continue per physician discretion.

Radiation therapy may be held for grade 4 cellulitis of the perineum or grade 4 neutropenia or other radiation-associated toxicity. Radiation should be restarted subsequent to recovery at the discretion of the treating radiation oncologist as per standard practice.

Table 11.1 Radiation therapy modifications based on adverse events

System/Organ/Class	Adverse Event	Dosage Change
Blood/lymphatic system disorders	Thrombocytopenia	Grade 2 – Continue at current dose Grade 3 – Hold until recovery ≤ grade 2 then resume Grade 4 – Hold until recovery ≤ grade 2 (platelets ≥ 75 x 10 ⁹ /L) then resume
	Neutropenia	Grade 3 or 4 – Hold until recovery ≤ grade 2 then resume
	Febrile Neutropenia	Grade 3 or 4 – Hold until resolution of fever and neutropenia ≤ grade 2. Hold until the ANC ≥ 1500/mm ³ and fever has resolved then resume
Gastrointestinal disorders	Diarrhea	Grade 1 or 2 – Continue at current dose Grade 3 – If grade 3 for >4 days, hold until recovery ≤ grade 2 then resume Grade 4 – Hold until recovery ≤ grade 2 then resume

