11.2 Chemotherapy

The patient will discontinue FOLFOX and be referred for treatment off protocol if the patient requires dose reduction beyond level -2 during cycles 1-5 of preoperative therapy or if FOLFOX is held due to toxicity for more than 30 days from the previous cycle.

The precise dose modification schema used and the symmetry of dose modification may be left to the discretion of the treatment physician.

Table 11.2 FOLFOX dose levels

Dose level*	5-FU infusion	5-FU bolus	Oxaliplatin
0	1200 mg/m ² /day x 2 days (2400 mg/m ² over 48 hours)	400 mg/m ²	85 mg/m ²
-1	960 mg/m ² /day x 2 days (1920 mg/m ² over 48 hours)	320 mg/m ²	65 mg/m ²
-2	800 mg/m ² /day x 2 days (1600 mg/m ² over 48 hours)	270 mg/m ²	50 mg/m ²
-3	680 mg/m ² /day x 2 days (1360 mg/m ² over 48 hours)	230 mg/m ²	40 mg/m ²

*Dose level 0 refers to the starting dose

Table 11.3 FOLFOX dose modifications based on adverse events

System/organ/class	Adverse event	Agent	Dosage change
Blood and lymphatic systemic disorders	Neutropenia grade ≥2 and/or Thrombocytopenia grade ≥ 2	5-FU Oxaliplatin	Hold up to 16 days until ANC ≥ 1200 K/mcL. If recovered in ≤ 16 days, then resume at next lower dose level. Hold up to 16 days until platelets ≥ 75,000 K/mcL. If recovered in ≤ 16 days, then resume at next lower dose level.
Gastrointestinal disorders	Nausea grade 2 Nausea grade 3	Oxaliplatin	Intensify antiemetic therapy and proceed with FOLFOX at current dose level. Maximal antiemetic therapy includes a 5-HT inhibitor in addition to Compazine, lorazepam, aprepitant, and dexamethasone If resolved to < grade 2 on day of treatment, may proceed with intensification of antiemetic therapy and current dose level of FOLFOX. If not resolved to < grade 2 on day of therapy, intensify antiemetic regimen

	Nausea grade 4	5-FU Oxaliplatin	and proceed with FOLFOX when resolved to < grade 2. May decrease oxaliplatin one dose level if not responsive to maximal antiemetic support.
Vomiting grade 2	If resolved to < grade 2 on day of treatment, may proceed with intensification of antiemetic therapy and current dose level of FOLFOX. If not resolved to < grade 2 on day of therapy, intensify antiemetic regimen and proceed with FOLFOX when resolved to < grade 2. Decrease oxaliplatin one dose level if not responsive to maximal antiemetic support.		

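### Table 11.3 prints both blood-count thresholds for restarting FOLFOX 1000 times too high (K/mcL where /mcL is meant)

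*Combined protocol and SAP*

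**What the plan says.** Table 11.3 in Section 11.2 covers neutropenia and thrombocytopenia of grade 2 or worse in one row. For neutrophils it says "Hold up to 16 days until ANC ≥ 1200 K/mcL", and for platelets "Hold up to 16 days until platelets ≥ 75,000 K/mcL". A patient who recovers within 16 days restarts one dose level lower.

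Three other places bear on these numbers:

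- Table 11.1 in Section 11.1 governs radiation. For thrombocytopenia it says "Grade 4 – Hold until recovery ≤ grade 2 (platelets ≥ 75 x 10 ⁹ /L) then resume", and for febrile neutropenia "Hold until the ANC ≥ 1500/mm ³ and fever has resolved then resume".
- Section 3.1.9 sets the entry limits: ANC of at least 1500/mm3 and platelets of at least 100,000/mm3.
- Section 11.2 takes a patient off FOLFOX and off protocol "if FOLFOX is held due to toxicity for more than 30 days from the previous cycle". Section 5.1 sets the cycle at 14 days.

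Section 5.1.2 and the text above the tables in Section 11.2 both leave the details of dose modification to the treating physician.

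**The concern.** K/mcL is thousands of cells per microlitre. The figures 1200 and 75,000 are of the size expected for counts per microlitre, so the K multiplies each by a further 1000. The resulting thresholds lie far above the counts a patient needs to enter the trial, and the platelet threshold disagrees with the radiation table in the same chapter.

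This row holds the protocol's only numeric blood counts for restarting FOLFOX, so it is a working treatment rule and not background text. Followed to the letter, a patient whose FOLFOX is held for low counts never qualifies to restart. If the hold then simply continues, the patient passes the 30-day limit and leaves protocol treatment. Section 11.1 also holds radiation whenever chemotherapy is held, so both parts of the study regimen depend on the row.

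**Working it through.** **Conversions.** 1 K/mcL = 1000/mcL. 1 mm3 = 1 mcL. 1 L = 10^6 mcL, so 1 x 10^9/L = 1000/mcL.

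**Platelets**

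- Table 11.3 as printed: 75,000 x 1000 = 75,000,000/mcL, which is 75,000 x 10^9/L.
- Table 11.1: 75 x 10^9/L ÷ 10^6 mcL/L = 75,000/mcL, or 75 K/mcL.
- Ratio: 75,000,000 ÷ 75,000 = 1000.
- Against the entry limit in Section 3.1.9: 75,000,000 ÷ 100,000 = 750.

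**ANC**

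- Table 11.3 as printed: 1200 x 1000 = 1,200,000/mcL.
- Against the entry limit in Section 3.1.9: 1,200,000 ÷ 1500 = 800.
- Against the same numeral without the K: 1,200,000 ÷ 1200 = 1000. This ratio assumes that the numeral is right and the unit wrong.

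**After deleting the K**

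| Quantity | Printed | Corrected | Same value in K/mcL | Comparison |
|---|---|---|---|---|
| Platelets | 75,000,000/mcL | 75,000/mcL | 75 | Equals Table 11.1 |
| ANC | 1,200,000/mcL | 1200/mcL | 1.2 | 1200 ÷ 1500 = 0.8 of the entry limit |

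The corrected ANC is plausible, but no other part of the protocol gives 1200. The other numeric ANC limits are 1500/mm3, for study entry and for restarting radiation after febrile neutropenia.

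**Length of the hold.** Count from Day 1 of the previous cycle and assume that the hold begins on the next scheduled Day 1. The 14-day cycle plus the 16-day maximum hold gives 14 + 16 = 30 days. Section 11.2 acts on more than 30 days, so a hold that ends on its 16th day just stays within the limit, and one that runs longer exceeds it. Table 11.3 does not itself say what follows if counts have not recovered after 16 days.

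**Number of patients affected.** The protocol gives no rate of held cycles, so this cannot be computed.

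**The case against.** The best defence is that the slip corrects itself. A restart threshold 750 or 800 times the entry limit cannot be acted on, the numerals are in the usual per-microlitre form, and Table 11.1 supplies the platelet value. Physicians also have explicit discretion over dose modification, so the off-protocol consequence arises only if someone waits for an impossible count. This stands, and it is why the point is minor. It does not make the entry right: the 30-day rule in Section 11.2 is mandatory, and staff should not have to rely on discretion to restart treatment at a sensible count.

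The ANC half is also less certain than the platelet half. No second source gives 1200, and the platelet match comes from a radiation rule for grade 4 thrombocytopenia, not from a chemotherapy rule. This stands too. The intended ANC value is an inference, and Table 11.1 is strong support for the platelet value without being a restatement of the same rule.

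Finally, the two 1500/mm3 limits serve other purposes, and a lower count for restarting chemotherapy at a reduced dose need not conflict with them. That is fair, and no conflict is claimed. Confirmation is worth asking for only because a correction to this cell should not be issued with its second number unchecked.

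**Conclusion.** The point holds and is minor. The unit in both cells is wrong. The platelet threshold is 1000 times the Table 11.1 value, and the ANC threshold is 1000 times too high on the assumption that 1200/mcL was intended. The same legible unit appears in both entries, so a fault in reading the PDF is unlikely.

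The literal consequence is that a held patient never restarts and eventually leaves protocol treatment. It is unlikely in practice, because staff would infer the intended counts, and it rests on the day-counting assumption and on the hold continuing beyond 16 days. The error does not lead to dosing at unsafe counts. The pCR endpoint, the precision-based sample size in Section 14 and the two-stage rule in Section 10.1 do not use these thresholds.

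**What to change.** In Table 11.3, delete the K in both places, so that the thresholds are ANC ≥ 1200/mcL and platelets ≥ 75,000/mcL. Keeping the unit and printing 1.2 and 75 would be equivalent. Before the correction is issued, the clinical team should confirm that 1200 is the ANC they intend.

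The cost is two unit corrections in one table row and one clinical confirmation, which can go with the next amendment. No procedures, visits or patients are added.

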Vomiting grade 3	Intensify antiemetic therapy and proceed with FOLFOX at current dose level. Maximal antiemetic therapy includes a 5-HT inhibitor in addition to Compazine, lorazepam, aprepitant, and dexamethasone		
Vomiting grade 4	If resolved to < grade 2 on day of treatment, may proceed with intensification of antiemetic therapy and current dose level of FOLFOX. If not resolved to < grade 2 on day of therapy, intensify antiemetic regimen and proceed with FOLFOX when resolved to < grade 2. May decrease oxaliplatin one dose level if not responsive to maximal antiemetic support.		
Diarrhea grade 2	If resolved to < grade 2 on day of treatment, may proceed with intensification of antiemetic therapy and current dose level of FOLFOX. If not resolved to < grade 2 on day of therapy, intensify antiemetic regimen and proceed with FOLFOX when resolved to < grade 2. Decrease oxaliplatin one dose level if not		
Diarrhea grade 3			

	
Diarrhea grade 4
 
Oral mucositis, esophagitis, gastritis, pharyngeal mucositis, small intestinal mucositis, colitis, rectal and/or anal mucositis grade 3
 
Oral mucositis, esophagitis, gastritis, pharyngeal mucositis, small intestinal mucositis, colitis, rectal and/or anal mucositis grade 4
	
responsive to maximal antiemetic support.
 
If resolved to < grade 2, intensify antidiarrheal therapy and proceed with FOLFOX at current dose level. If not resolved to < grade 2, hold FOLFOX, intensify antidiarrheal therapy and proceed with FOLFOX when resolved to < grade 2.
 
If resolved to < grade 2, intensify antidiarrheal therapy and proceed with FOLFOX, decreasing 5FU and oxaliplatin one dose level. If not resolved to < grade 2, hold FOLFOX, intensify antidiarrheal therapy and proceed with FOLFOX decreasing 5FU one dose level when resolved to < grade 2.
 
If resolved to < grade 2, intensify antidiarrheal therapy and proceed with FOLFOX, decreasing 5FU and oxaliplatin one dose level. If not resolved to < grade 2, hold FOLFOX decreasing 5FU and oxaliplatin one dose level when resolved to < grade 2.
 
Hold FOLFOX until mucositis improves to < grade 2 then resume with one dose level reduction of 5-FU and the previous dose level of oxaliplatin
 
Hold FOLFOX until mucositis improves to < grade 2 then resume with two dose levels reduction of 5-FU and the previous dose level of oxaliplatin

--	---	--

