Pulmonary disorders	Cough, dyspnea, hypoxia, pneumonitis or pulmonary infiltrates grade 3+	5-FU Oxaliplatin	Hold oxaliplatin until interstitial lung disease is ruled out. Continue 5-FU/leucovorin. Discontinue study if interstitial lung disease is confirmed.
Thrombotic microangiopathy	Hemolytic uremic syndrome grade 3+	5-FU Oxaliplatin	Discontinue oxaliplatin. Continue 5-FU/leucovorin.
Immune system disorders	Allergic reaction grade 1 Allergic reaction grade 2 Allergic reaction grade 3 or 4	Oxaliplatin Leucovorin	Decrease infusion rate by 50% until symptoms resolve, then resume at initial planned rate. Stop FOLFOX infusion. Administer H1 and/or H2 blockers and/or steroids according to local medical site policy. Restart infusion when symptoms resolve and pretreat before all subsequent doses. Stop infusion. Discontinue FOLFOX.
Skin and subcutaneous tissue disorders	Extravasation	Oxaliplatin	Extravasation of oxaliplatin has been associated with necrosis. If extravasation is suspected, stop the FOLFOX infusion and restart at another site.
Neurological	Neurotoxicity grade 2 persisting between treatment cycles Neurotoxicity grade 3 resolving to ≤grade 2 between treatment cycles Neurotoxicity grade 3 persisting between treatment cycles Neurotoxicity grade 4	Oxaliplatin	Continue FOLFOX with previous dose level of 5-FU and one dose level reduction of oxaliplatin for all subsequent cycles. Continue FOLFOX with previous dose level of 5-FU and one dose level reduction of oxaliplatin for all subsequent cycles. Discontinue oxaliplatin. Continue 5-FU/leucovorin. Discontinue oxaliplatin. Continue 5-FU/leucovorin.
Other non-hematologic	Grade 3 or 4	5-FU Oxaliplatin Leucovorin	Hold FOLFOX until toxicity ≤grade 1 then resume with one dose level reduction of both 5-FU and oxaliplatin.

The following describe actions in the Dosage Change column:

Omit = Treatment is not given for this cycle
Hold = Treatment can be made up as part of this cycle
Discontinue = Treatment is totally stopped

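### Table 11.3, grade 3 diarrhoea: the patient whose diarrhoea has not resolved restarts on more oxaliplatin than the patient who recovered sooner

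*Combined protocol and SAP*

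**What the plan says.** Table 11.3 in section 11.2 sets out FOLFOX changes by adverse event. For grade 3 diarrhoea it distinguishes two situations.

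- **Already below grade 2:** "intensify antidiarrheal therapy and proceed with FOLFOX, decreasing 5FU and oxaliplatin one dose level".
- **Not yet below grade 2:** "hold FOLFOX, intensify antidiarrheal therapy and proceed with FOLFOX decreasing 5FU one dose level when resolved to < grade 2".

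The neighbouring diarrhoea actions differ in this respect. At grade 2 the resolved branch continues at the current dose, and the other branch is to "hold FOLFOX, intensify antidiarrheal therapy and proceed with FOLFOX when resolved to < grade 2", again with no reduction. At grade 4 the resolved branch lowers both drugs, and so does the other: "hold FOLFOX decreasing 5FU and oxaliplatin one dose level when resolved to < grade 2".

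Two clauses leave room for judgement. Section 5.1.2 says "Chemotherapy dose modification is at the discretion of the treating medical oncologist", with removal from the study below level -2. Section 11.2, just before the dose tables, says "The precise dose modification schema used and the symmetry of dose modification may be left to the discretion of the treatment physician".

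**The concern.** Within a single action, the set of drugs reduced runs against the persistence of the toxicity. A patient whose grade 3 diarrhoea has settled loses a level of both drugs. A patient whose diarrhoea has not settled, so that treatment must be held, loses a level of 5-FU only. No rationale is given.

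A physician who follows the printed default would restart the patient with the more persistent toxicity at the higher oxaliplatin dose. One who looks to the table for whether grade 3 diarrhoea calls for an oxaliplatin reduction gets two answers.

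Dose level also affects who stays on protocol, because a reduction beyond level -2 in cycles 1 to 5 ends protocol treatment. The wording could therefore occasionally decide retention as well as dose.

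**Working it through.** The plan states no figure to reproduce. The check is a reading of Table 11.3 followed by the doses from Table 11.2.

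**1. Is this the grade 3 diarrhoea action?** The gastrointestinal block lists nausea (3 grades), vomiting (3), diarrhoea (3) and the mucositis group (2): 3 + 3 + 3 + 2 = 11 events. It has 11 action paragraphs. Matched in order, the eighth is diarrhoea grade 3. Both branches lie in that one paragraph, so displaced table columns cannot have produced the mismatch.

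**2. The branches side by side**

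| Diarrhoea | Already below grade 2 | Held until below grade 2 |
|---|---|---|
| Grade 2 | no reduction | no reduction |
| Grade 3 | 5-FU and oxaliplatin down one level | 5-FU down one level |
| Grade 4 | 5-FU and oxaliplatin down one level | 5-FU and oxaliplatin down one level |

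Only grade 3 differs between branches.

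**3. Other rows of Table 11.3.** For the event "Neurotoxicity grade 3 persisting between treatment cycles" oxaliplatin is discontinued, whereas grade 3 neurotoxicity that resolves to grade 2 or less costs one oxaliplatin level; there the stronger action follows persistence. Grade 3 mucositis is held, "then resume with one dose level reduction of 5-FU and the previous dose level of oxaliplatin". A 5-FU-only reduction is therefore not odd in itself, but the mucositis row says explicitly what happens to oxaliplatin, and the held diarrhoea branch does not.

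**4. Doses.** Table 11.2, in mg/m2, for levels 0, -1 and -2: oxaliplatin 85, 65, 50; 5-FU infusion 2400, 1920, 1600; 5-FU bolus 400, 320, 270.

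| Both drugs starting at | 5-FU on restart, either branch (infusion / bolus) | Oxaliplatin, resolved | Oxaliplatin, held | Difference | Ratio |
|---|---|---|---|---|---|
| Level 0 | 1920 / 320 | 65 | 85 | 20 | 85/65 = 1.31 |
| Level -1 | 1600 / 270 | 50 | 65 | 15 | 65/50 = 1.30 |

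**5. Retention.** Take a patient in cycles 1 to 5 with oxaliplatin at -2 and 5-FU at a higher level, for example after neurotoxicity reductions. Read literally, the resolved branch moves oxaliplatin to -3 and ends protocol treatment; the held branch keeps the patient on. This is probably rare.

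**The case against.** The best defence is that the table is guidance. Whether the two drugs come down together is a question of symmetry, which section 11.2 may leave to the physician, so either course is compliant. That limits the harm. But freedom to depart from a default does not make a contradictory default coherent, and this is the only default printed.

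Other safeguards also count. Both branches give drug only once diarrhoea is below grade 2. Section 11.1 holds radiation when chemotherapy is held. Section 11.2 ends FOLFOX if it is held for toxicity more than 30 days from the previous cycle, and section 12.0 lists a grade 3-4 event lasting three weeks or more as a reason to discontinue. The most persistent cases may thus never restart. On a 14-day cycle, however, the 30-day limit still allows a delay of up to 30 - 14 = 16 days.

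The 31% is also per dose and ignores the delay. If a hold of d days stretches the 14-day interval (d is an assumption), oxaliplatin per day over that interval is 85/(14 + d) held against 65/14 resolved. These are equal at d = 14 × 85/65 - 14 = 4.3 days; from level -1, at 14 × 65/50 - 14 = 4.2 days. With a 7-day hold the held patient receives 85/3 = 28.3 mg/m2 per week against 65/2 = 32.5, about 13% less. That is a fair qualification for one interval. In later cycles the per-dose excess remains if doses are unchanged.

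Finally, mucositis may be a closer analogue than neurotoxicity, and it supports a 5-FU-only reduction after a hold. This stands as a reason not to presume which branch is the mistake; it does not explain why the resolved branch reduces more.

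**Conclusion.** The inconsistency is real and lies in an operative dosing rule. Followed as printed, and with both drugs at the same level beforehand, grade 3 diarrhoea that required a hold leads to 30 to 31% more oxaliplatin per dose on restart (15 to 20 mg/m2) than grade 3 diarrhoea that had already resolved, with identical 5-FU. This rests on the doses in Table 11.2 and on matching events to actions in order; the conflict between branches would remain even if that row assignment were disputed.

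The patient-safety relevance is low but not nil. The documents give no rate of grade 3 diarrhoea, so the number affected among the 30 planned patients cannot be estimated. Nor do they show whether oxaliplatin was left out of one branch or added by mistake to the other. The definition of pathological complete response, the sample size and the stopping rule are unaffected.

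**What to change.** The investigators should confirm which reduction they intend and correct the grade 3 diarrhoea action in Table 11.3:

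- **If both drugs are to be reduced:** add *and oxaliplatin* after 5FU in the held branch, so that it matches the resolved branch and the grade 4 action.
- **If only 5-FU is to be reduced:** delete *and oxaliplatin* from the resolved branch.

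The discretion clauses in sections 5.1.2 and 11.2 can stay as they are. The cost is a one-line change in the next amendment, with no effect on sample size, visit schedule or endpoints.
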